1.2 QOL Tools

- 1.21 QOL is an important outcome and covariate in this trial because the treatments are expected to differ in terms of their symptom profiles and impact on patient well-being. Previous data has indicated that the most prevalent QOL issues with these patients are fatigue, pain, weight loss, and other symptoms, as well as more general aspects of QOL such as ability to enjoy life and contentedness in QOL (Odom et. al. 2010). We hypothesize that patients receiving regorafenib will experience greater deficits in QOL as reflected by scores on the HSF14, the BFI and the LASA. These questionnaires have specific application to this population.

The HSF14 has been specifically designed to capture changes in QOL related to PPES. Cronbach's alpha for this questionnaire is 0.93. It involves 14 questions

with three domains: hand, feet, and social. The final score for this questionnaire ranges from 2-100, where a higher score indicates greater QOL impairment (Sibaud et. al., 2011). For comparison to other QOL questionnaires, the HSF14 will be converted to a 0-100 scale, where a higher score indicates better QOL.

The Brief Fatigue Inventory (BFI), a 9-item questionnaire, has been validated as a short and comprehensive instrument to assess severity of fatigue and fatigue-related impairment in cancer patients. The reliability estimated with Cronbach's alpha ranges from 0.82 to 0.97. Recently, both the German version and the Japanese version of the BFI has been validated with test-reliability (mean scores of 0.93) and impairment (mean scores of 0.87) for the German version and reliability with Cronbach's alpha at 0.96 for the Japanese version. Minor differences were seen in the validation of the German version compared to the original version.

Linear Analogue Self Assessment (LASA) items have been validated as general measures of global QOL dimensional constructs in numerous settings (Grunberg et al., 1996; Gudex et al, 1996; Hyland et al., 1996; Srivatanakul, 1983; Wewers, 1990). A series of LASA items have been constructed and validated at Mayo Clinic for use in cancer patients (Bretscher et al, 1999). These items have been seen to be important prognostic factors for cancer patient survival and should be included as covariates in survival analysis (Sloan, JCO, 2012).

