5.0 Stratification Factors: None

6.0 Registration/Randomization Procedures

6.1 Randomization Procedures

- 6.11 To randomize a patient, access the ACCRU web page at [REDACTED] click on “Training Page” and enter the registration/randomization application. The registration/randomization application is available 24 hours a day, 7 days a week. Back up and/or system support contact information is available on the Web site. If unable to access the Web site, call the Academic and Community Cancer Research United (ACCRU) Registration Office at [REDACTED] between the hours of 8 a.m. and 4:30 p.m. Central Time (Monday through Friday).

The instructions for the registration/randomization application are available by using the Help button. Prior to initiation of protocol study intervention, this process must be completed in its entirety and an ACCRU subject ID number must be available as noted in the instructions. It is the responsibility of the individual and institution registering the patient to confirm the process has been successfully completed prior to release of the study agent. Patient registration via the registration/randomization application can be confirmed in any of the following ways:

- Contact the ACCRU Registration Office [REDACTED]. If the patient was fully registered, the ACCRU Registration Office staff can access the information from the centralized database and confirm the registration.
- Refer to “Instructions for Remote Registration” in section “Finding/Displaying Information about A Registered Subject.”

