6.12 Correlative Research

- A mandatory correlative research component is part of this study. The patient will be automatically registered onto this component (see Sections 3.0 and 14.0).
- A mandatory banking component is part of this study. The patient will be automatically registered onto this component (see Sections 3.0 and 14.0).

- 6.13 Documentation of IRB approval must be on file in the Registration Office before an investigator may register any patients.

In addition to submitting initial IRB approval documents, ongoing IRB approval documentation must be on file (no less than annually) at the Registration Office ([REDACTED]). If the necessary documentation is not submitted in advance of attempting patient registration, the registration will not be accepted and the patient may not be enrolled in the protocol until the situation is resolved.

When the study has been permanently closed to patient enrollment, submission of annual IRB approvals to the Registration Office is no longer necessary.

- 6.14 Prior to accepting the registration/randomization, the registration/randomization application will verify the following:
- IRB approval at the registering institution
 - Patient eligibility
 - Existence of a signed consent form
 - Existence of a signed authorization for use and disclosure of protected health information
- 6.15 At the time of randomization, the following will be recorded:
- Patient has given permission for ACCRU to give his/her sample(s) to outside researchers.
- 6.16 Treatment cannot begin prior to randomization and must begin ≤ 7 days after randomization.
- 6.17 Pretreatment tests/procedures (see Section 4.0) must be completed within the guidelines specified on the test schedule.
- 6.18 All required baseline symptoms (see Section 10.5) must be documented and graded.
- 6.19a Treatment on this protocol must commence at an ACCRU institution under the supervision of a medical oncologist.
- 6.19b Blood draw kit is available on site.
- 6.19c Patient questionnaire booklet is available on site; copies are not acceptable for this submission.
- 6.2 Randomization Procedures
- 6.21 The registering membership will be used as the only stratification factor for this study.

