12.0 Descriptive Factors

12.1 BRAF analysis done: Yes vs. no.

12.11 If yes, wild-type vs. mutated.

12.2 KRAS analysis done: Yes vs. no.

12.21 If yes, wild-type vs. mutated.

12.3 ECOG Performance Status: 0 vs. 1.

12.4 Age: <70 vs. ≥70.

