16.3 Statement for Primary Endpoint

The primary endpoint is the proportion of patients in each arm who complete 2 cycles of protocol treatment and initiate cycle 3. The proportion will be calculated among evaluable patients separately by arm (Arm A vs. Arm B). Evaluable patients are defined as patients who are eligible, consented, received any protocol treatment. In the CORRECT trial, among patients who were randomized to regorafenib, 45% continued treatment beyond cycle 2. Other than disease progression, majority of patients discontinued regorafenib due to adverse events not associated with progression. It was noted that most adverse events occurred during Cycles 1-2 of the treatment (Grothey A et. al., 2013, Lancet). Assuming 45% of patients would complete 2 cycles of protocol treatment and initiate cycle 3 in the control (standard dose; pooled arms B1 and B2) group, and desiring an improvement to 63% in the experimental (starting low dose) group (pooled arms A1 and A2), a one-sided test with $\alpha = 0.20$ and power of 80% will require a sample size of 110 patients enrolled to both regorafenib arms (A and B). We will enroll 13 additional patients to account for ineligibility, cancellation, major treatment violation, or other reasons. Maximum projected accrual is therefore 123 patients. A Fisher exact test will be used to detect a difference in proportion of patients who complete 2 cycles of protocol treatment and initiate cycle 3 between arms (starting low dose [pooled arm A1 and A2] vs. standard dose [pooled arm B1 and B2]). The proportion of patients who complete 2 cycles of protocol treatment and initiate cycle 3 will be computed by arm with its 95% confidence interval using exact method.

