16.4 Supplementary Analysis Plans (includes all secondary and translational goals)

- 16.41 Overall survival (OS) is defined as time from randomization to death due to any cause. OS will be estimated with Kaplan-Meier survival curves and differences between regorafenib arms (A vs. B) tested using log-rank tests, though we note these analyses are not powered for formal non-inferiority assessments. See Section 2.21.
- 16.42 Progression-free survival (PFS) is defined as the time from randomization to the earlier of disease progression or death due to any cause, where progressed disease (PD) is as defined by RECIST 1.1 (see Section 11.0). PFS will be estimated with Kaplan-Meier survival curves and differences between regorafenib arms (A vs. B) tested using log-rank tests, though we note these analyses are not powered for formal non-inferiority assessments. See Section 2.21.
- 16.43 Time to progression (TTP) is defined as the time from randomization to disease progression, where progressed disease (PD) is defined by RECIST 1.1 (see Section 11.0). TTP will be estimated with Kaplan-Meier survival curves and differences between regorafenib arms (A vs. B) tested using log-rank tests, though we note these analyses are not powered for formal non-inferiority assessments. See Section 2.21.
- 16.44 The cumulative (total) dose of regorafenib received by patients and dose intensity in the first two cycles will be summarized with descriptive statistics and compared between regorafenib arms (A vs. B) using the t-test (if approximately normally distributed) or the Wilcoxon rank sum test (if not approximately normally distributed). Dose intensity is defined as the cumulative (total) dose of regorafenib divided by the expected total dose. See Section 2.22.
- 16.45 The proportion of patients overall and within each arm experiencing grade 3 or 4 HFS or fatigue will be computed with 95% confidence intervals, and differences between regorafenib dosing strategies (pooled across HFS strategies) tested using a Fisher Exact test. The incidence of grade 3 or 4 HFS will also be descriptively compared between those receiving a pre-specified preemptive vs. reactive approach for hand and foot syndrome (pooled across dosing strategies), and tested using a Fisher Exact test. See Section 2.24. Adverse event reports will be shared with [name] of Memorial Sloan Kettering Cancer Center 1-2 times per month for review.

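### Section 1.2 calls for LASA quality-of-life items as covariates in survival analysis, but 16.41 to 16.43 plan only unadjusted log-rank tests, and Section 5.0 conflicts with 6.21 on stratification

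*Combined protocol and SAP*

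**What the plan says.** **Rationale.** Section 1.2 names quality of life as both an outcome and a covariate for this trial. It describes the LASA items as "important prognostic factors for cancer patient survival and should be included as covariates in survival analysis".

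**Survival analysis.** Section 16.41 reads "OS will be estimated with Kaplan-Meier survival curves and differences between regorafenib arms (A vs. B) tested using log-rank tests". Sections 16.42 (PFS) and 16.43 (TTP) use the same wording. All three add that the analyses are not powered for formal non-inferiority.

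**Primary endpoint.** Section 16.3 applies a Fisher exact test to "starting low dose [pooled arm A1 and A2] vs. standard dose [pooled arm B1 and B2]". No covariate or stratum is named there or elsewhere in Section 16. The reference list includes a paper on a stratified Fisher exact test, but Section 16 does not use it.

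**Baseline data.** Section 12.0 lists "ECOG Performance Status: 0 vs. 1" with age, KRAS and BRAF as descriptive factors. Section 4.0 schedules questionnaires at baseline, and 16.46 compares LASA change from baseline, so a baseline LASA score is expected to exist.

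**Allocation.** Section 5.0 reads "Stratification Factors: None". Section 6.21 reads "The registering membership will be used as the only stratification factor for this study", and 6.22 describes a Pocock and Simon procedure that balances on stratification factors.

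**Missing data.** Section 16.8 drops patients with missing data from the relevant analysis and allows no imputation.

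**The concern.** The protocol states a covariate analysis in its rationale and gives no method for it. If one is added once results are known, the choice of covariates and model form is open.

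Performance status is protected by neither design nor analysis. The only allocation factor named is registering membership, and no planned model contains PS. With about 55 patients per dosing arm, a chance imbalance in PS passes straight into the reported PFS and OS estimates. Those estimates matter because Section 1.1 sets out to keep the known benefit of regorafenib while improving tolerability. Readers will look to the survival curves for the first half of that aim, even though they are secondary and not powered for it.

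The conflict between 5.0 and 6.21 leaves an analyst unsure what was balanced, and therefore which stratum a stratified analysis should respect.

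**Working it through.** **1. The plan's own figure.** Inputs from 16.3: 45% vs 63%, one-sided alpha 0.20, and "and power of 80% will require a sample size of 110 patients". Exact enumeration of the one-sided Fisher test gives power 0.797 at 54 per arm and 0.804 at 55 per arm, so 110 reproduces. Its actual one-sided size at 55 per arm is about 0.146, below the nominal 0.20. Inflation: 110 / (1 − 0.10) = 122.2, rounded up to 123. Nothing here needs correcting.

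**2. Power for survival.** The documents give no OS hazard ratio, covariate effect or test level for 16.41 to 16.43, so all three are assumed. Simulation: 55 per arm, about 80 deaths, adjusted hazard ratio 0.70, one-sided 0.20, one baseline covariate.

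| Covariate HR per SD | Log-rank power | Adjusted Cox power | Gain (points) | Unadjusted HR |
|---|---|---|---|---|
| 1.3 | 0.74 | 0.76 | 2 | 0.71 |
| 1.5 | 0.72 | 0.77 | 5 | 0.72 |
| 2.0 | 0.68 | 0.77 | 9 | 0.75 |

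A separate simulation with PS hazard ratio 1.5 to 2 and QOL hazard ratio 1.5 to 1.8 gave gains of 0 to 5 points. The gain depends on the test level. At two-sided 0.05 with a hazard ratio of 0.60, the same three covariate strengths gave 0.586 vs 0.606, 0.553 vs 0.602 and 0.438 vs 0.593, or gains of about 2, 5 and 16 points. Under the null the log-rank test held its size (about 0.20 one-sided).

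**3. Chance imbalance in PS.** Treat the PS 1 counts as independent binomials, 55 per arm.

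| Assumed share PS 1 | Imbalance ≥ 10 points | Imbalance ≥ 15 points |
|---|---|---|
| 50% | 29.4% | 10.5% |
| 30% | 25% | 8% |

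These count either direction. In one given direction, 15 points or more has probability of about 10.5 / 2 = 5%.

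**4. Effect of a 15-point imbalance.** Shift in the log hazard ratio ≈ 0.15 × ln(PS hazard ratio).

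- PS hazard ratio 1.5: 0.15 × 0.405 = 0.061; exp(0.061) = 1.06, a shift of about 6%.
- PS hazard ratio 2: 0.15 × 0.693 = 0.104; exp(0.104) = 1.11, a shift of about 11%.

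With 80 deaths the standard error of the log hazard ratio is about 2 / √80 = 0.22, so the larger shift is 0.104 / 0.22 ≈ 0.47 of a standard error.

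**5. Primary endpoint.** At 110 patients and one-sided 0.20, Fisher power is about 0.80 and an unadjusted z test gives about 0.855. Adjusted logistic regression gives 0.865, 0.88 and 0.90 for an assumed prognostic odds ratio per SD of 1.5, 2 and 3. The covariate itself therefore adds about 1 to 4 points; the rest comes from leaving the conservative exact test. These figures are for a generic covariate, not PS specifically.

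Stratifying by membership (Cochran-Mantel-Haenszel, 112 patients) gives 0.86 to 0.87 when the assumed between-membership logit SD is 0 to 0.5, and about 0.90 when it is 1.0. The unadjusted z test gives 0.86 to 0.88 over the same range. With SD 1.0 the size of the Fisher test falls to about 0.12 to 0.13. Adding PPES strategy as a further stratum gains under one point.

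**The case against.** The strongest reply is that nothing planned is wrong. Randomisation-based tests already allow for chance imbalance, the log-rank test holds its size, and 110 reproduces. Survival is secondary in a randomised phase II trial. The covariate effects are assumptions, and eligibility is already restricted to PS 0 or 1. All of this stands, and it caps the weight of the point.

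Part of the gap between unadjusted and adjusted hazard ratios (for example 0.75 against an adjusted 0.70) is non-collapsibility. The two are different estimands, and the gap does not show the log-rank test to be in error. That also stands.

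A LASA-adjusted model has its own risk: under 16.8 a patient with a blank baseline booklet would drop out of the OS model. This is a fair criticism of a naive fix and is dealt with below.

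A reader might infer several stronger things that the documents do not support:

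- **That Section 1.2 requires adjustment for ECOG PS, age or KRAS, or of the primary endpoint.** It speaks only of quality of life, and its explicit instruction concerns LASA items in survival analysis. Using PS descriptively is consistent with Section 12.0.
- **That every comparison ignores baseline.** The LASA analysis in 16.46 uses change from baseline, and the HFS14 analysis is to account for time-dependence.
- **That PPES strategy was overlooked in the A vs B test.** Pooling is stated in 2.11, 16.1 and 16.3, allocation is 1:1:1:1, and the strategy has its own comparisons in 16.45 and 16.46.

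What the reply does not answer is the mismatch between 1.2 and 16.41 to 16.43, or the conflict between 5.0 and 6.21.

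**Conclusion.** The point holds as an internal inconsistency with a modest statistical cost. Section 1.2 and Sections 16.41 to 16.43 do not agree, and 5.0 and 6.21 cannot both be right. Adjusting for PS is a statistical recommendation, not something the protocol promised.

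The cost is lost precision and estimates left uncorrected for chance imbalance. It is not bias, type I error inflation or a wrong sample size. The size rests on assumptions the documents cannot confirm: the share of PS 1 patients, the PS and QOL hazard ratios, the OS effect, the number of deaths and the test level. Within the ranges shown, the survival power gain is usually 0 to 5 points and about 9 at one-sided 0.20 with a strong covariate; only a strong covariate combined with a stricter level takes it higher. The change is worth making because it is nearly free and removes a later choice, not because the planned analyses fail.

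**What to change.** 1. Keep the log-rank tests and the primary Fisher test as planned.
2. Add to 16.41 to 16.43 a pre-specified supportive Cox model for A vs B with ECOG PS and baseline LASA overall QOL as covariates, stratified by registering membership with a stated rule for pooling small memberships. PPES strategy may be an optional term.
3. Add to 16.3 a supportive estimate of the A vs B difference adjusted for ECOG PS and membership.
4. Make an exception to 16.8 so that patients with a missing baseline LASA stay in the model, by single imputation of that baseline covariate or a missing indicator.
5. Reconcile 5.0 with 6.21.

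Cost: a few sentences and a few more model runs on data already scheduled for collection, with no extra patients. The adjusted hazard ratio is a conditional estimate and must be labelled as such beside the unadjusted result, so that the two are not read as rival answers to one question.

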2.2 Secondary

- 2.21 Evaluate outcome measures for efficacy in each arm including progression-free survival (PFS), time to progression (TTP), and overall survival (OS).
- 2.22 Compare between arms the cumulative dose and dose intensity received within the first two cycles.
- 2.23 Evaluate the proportion of patients in each arm that exhibit grade 3 Palmar-plantar erythrodysesthesia syndrome (PPES) and/or fatigue, and make comparisons between regorafenib dosing strategies and pre-emptive vs. reactive strategies to address PPES.
- 2.24 Compare QOL between treatment arms (regorafenib dosing strategies and pre-emptive vs. reactive PPES strategies) as measured by the HFS14, BFI, and LASA questionnaires.

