 5. Patient questionnaires will be completed at baseline (appendices IV and V only), Cycle 1 Day 14, Cycle 2 Day 1, Cycle 2 Day 14 and Cycle 2 Day 28. Cycle 2 Day 14 and Cycle 2 Day 28 patient questionnaire can be sent home with the patient to complete and return at their next clinic visit if needed. Patient questionnaire booklets **must** be used; copies are not acceptable for this submission.
 6. Performed at screening and then as needed.
 7. AST, ALT and total bilirubin will be checked at baseline and every other week during Cycles 1 and 2.
 8. +/- 1 day. Applies to days 1, 8, 15, and 22; includes baseline tests and procedures for Day 1 Cycle 1.
 9. If patient goes off study during Cycle 1 and last CT scan was done >28 days prior, the CT scan must be done.
 10. If a subject is on warfarin with stable PT/INR at baseline, the PT/INR should be assessed on Day 5 (+/- 3 days). If value is above the therapeutic range, the dose should be modified and the assessment should be repeated weekly until it is stable.
 11. Hematology and chemistry tests to be done prior to each cycle.
 12. If baseline history, exam, weight, ECOG PS, and blood pressure were performed ≤ 3 days of Cycle 1 Day 1, they do not need to be repeated for Cycle 1 Day 1.
 13. It is suggested that patients start treatment Tuesday-Friday to avoid PK collection on Sundays.
- R Research funded (see Section 19.0)

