- 6.22 After the patient has been registered into the study, the patient will be assigned to one of the following treatment groups, in 1:1:1:1 fashion, using the Pocock and Simon dynamic allocation procedure which balances the marginal distributions of the stratification factors between the treatment groups (Pocock-Simon, 1975).
- Arm A 1: Regorafenib Cycle 1: 80 mg daily Week 1/120 mg daily Week 2/160 mg daily week 3 then 1 week off followed by Cycle 2+ (160 mg for 21 days/1 week off) + pre-emptive strategy for PPES starting Cycle 1 Day 1
 - Arm A 2: Regorafenib Cycle 1: 80 mg daily week 1/120 mg daily week 2/160 mg daily week 3 then 1 week off followed by Cycle 2+ (160 mg for 21 days/then 1 week off) + reactive strategy for PPES
 - Arm B 1: Regorafenib 160 mg daily for 21 days/then 1 week off + pre-emptive strategy for PPES starting Cycle 1 Day 1
 - Arm B 2: Regorafenib 160 mg daily for 21 days/then 1 week off + reactive strategy for PPES

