- 16.46 Furthermore, patients will be descriptively compared between treatment arms and between HFS treatment strategies (pre-emptive vs. reactive) according to self-reported outcomes given on the HFS14 questionnaire. See Section 2.24. Results from the cycle 1 and 2 HSF14 questionnaires will also be summarized descriptively as they relate to the pre-emptive versus reactive PPES strategies, with comparisons made within and between arms using the t-test or Wilcoxon rank sum test as appropriate, as well as taking time-dependence into account. Changes in QOL (according to the LASA questionnaire as measured by the overall QOL question) from baseline will also be compared between the treatment arms using the t-test or Wilcoxon rank sum test. We hypothesize that patients receiving regorafenib will experience greater deficits in QOL as reflected by scores on the HSF14, the BFI and the LASA. These questionnaires have specific application to this population. See Section 2.24.
- 16.47 Pharmacokinetic Analysis
- The samples will be analyzed for the regorafenib concentrations using liquid chromatography mass spectrometry, with the anticipated method being a modified version

of that published by Van Erp et al. The samples will be analyzed for M2 and M5, if cost-free standards can be obtained from Bayer.

After quantitation, the average regorafenib concentration will be calculated by arms (Arm A vs. B) at each time point.

As exploratory analysis, this average concentration will be correlated with toxicity and efficacy endpoints. Further descriptive characteristics of the pharmacokinetics will also be calculated. An example includes (but is not limited to) within-patient variability in the trough concentrations pharmacokinetic parameters will also be calculated, both overall and within cycles, as a ratio of the maximum:minimum value.

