16.8 Missing Data

Patients with missing data will be excluded from relevant analyses; no imputation of missing data will be performed.

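### Section 16.46 tests LASA change from baseline without adjusting for the baseline score; ANCOVA on that score would cut the variance by 15% to 35% if r is 0.7 to 0.3 and the SDs are equal

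*Combined protocol and SAP*

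**What the plan says.** Goal 2.24 is to compare QOL between dosing strategies and between PPES strategies "as measured by the HFS14, BFI, and LASA questionnaires". Section 1.21 gives QOL weight: "QOL is an important outcome and covariate in this trial because the treatments are expected to differ in terms of their symptom profiles".

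The LASA analysis is one sentence in 16.46. It opens "Changes in QOL (according to the LASA questionnaire as measured by the overall QOL question" and continues that these changes "from baseline will also be compared between the treatment arms using the t-test or Wilcoxon rank sum test". It gives no covariate and no visit. The same section speaks of allowing for time-dependence, but in the HFS14 sentence, not the LASA one.

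Footnote 5 of the Test Schedule (4.0) sets the visits: "Patient questionnaires will be completed at baseline (appendices IV and V only), Cycle 1 Day 14, Cycle 2 Day 1, Cycle 2 Day 14". The last form is due on C2D28. That is a baseline and four post-baseline forms.

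Within Section 16, BFI appears only in a hypothesis sentence, with no test, summary measure or visit. The fatigue analysis in 16.45 concerns grade 3 or 4 adverse events, not the BFI score.

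Section 16.8 adds: "Patients with missing data will be excluded from relevant analyses; no imputation of missing data will be performed".

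**The concern.** To compute a change from baseline, the baseline score must be in hand. Once it is, subtracting it is one way to use it and regressing on it is another. Subtraction fixes the coefficient on baseline at 1, whereas ANCOVA estimates it. When baseline and follow-up correlate only moderately, subtraction adds baseline noise that regression would leave out, and the interval for the arm difference is wider than the same data allow.

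The trial asks whether a gentler start improves tolerability, and patient-reported QOL bears directly on that. The comparison has no stated power, so precision given away is not made up elsewhere.

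The unnamed visit is a smaller matter of specification, but it has to be settled for any adjusted analysis to be written down, because the four forms do not measure the same state. Section 6.22 plans Arm A as "80 mg daily Week 1/120 mg daily Week 2/160 mg daily week 3 then 1 week off followed by Cycle 2" and the standard-dose arm as "Arm B 1: Regorafenib 160 mg daily for 21 days/then 1 week off". By that schedule C1D14 falls at 120 mg in Arm A and 160 mg in Arm B. C2D14 is on drug in both arms. C2D1 follows the week off and C2D28 ends it.

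**Working it through.** **The plan's own figure.** The documents state no sample size, SD, correlation or power for LASA or BFI, so there is no QOL figure to reproduce. The only stated size is 110 patients for the primary endpoint (16.3: 45% against 63%, one-sided 0.20, 80% power, Fisher exact test). It reproduces: exact power is 79.7% at 54 per arm and 80.4% at 55 per arm. With 1:1:1:1 allocation, the pooled A against B comparison has 55 per arm, and I use that below. The percentage savings do not depend on this number.

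**Assumed inputs.** r is the correlation between baseline and follow-up LASA, and k is the ratio of follow-up SD to baseline SD. The documents give neither. I take r = 0.3, 0.5 and 0.7 and k = 0.8, 1 and 1.25.

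**Equal SDs (k = 1).**
- Variance of a change score: 2(1-r) SD².
- Residual variance after regression on baseline: (1-r²) SD².
- Ratio: (1-r²)/[2(1-r)] = (1+r)/2, so the saving is (1-r)/2.
- Standard error of the arm difference at 55 per arm, no loss: sqrt(2(1-r) × 2/55) for change and sqrt((1-r²) × 2/55) for ANCOVA. The 95% half-width is 1.96 times this.

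| r | SE, change (SD) | SE, ANCOVA (SD) | 95% half-width, change to ANCOVA (SD) | Variance saved | Change-score N giving the same precision, 110 × 2/(1+r) |
|---|---|---|---|---|---|
| 0.3 | 0.226 | 0.182 | 0.44 to 0.36 | 35% | 169 |
| 0.5 | 0.191 | 0.165 | 0.37 to 0.32 | 25% | 147 |
| 0.7 | 0.148 | 0.136 | 0.29 to 0.27 | 15% | 129 |

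A simulation at 55 per arm (8,000 replicates, regression slope estimated from the data) gave savings of 34%, 27% and 14%, in line with the formula.

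**Unequal SDs.** With baseline SD set to 1, the change score has variance 1 + k² - 2rk and the ANCOVA residual has variance k²(1-r²). The saving is 1 - k²(1-r²)/(1 + k² - 2rk).

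| k | r = 0.3 | r = 0.5 | r = 0.7 |
|---|---|---|---|
| 0.8 | 50% | 43% | 37% |
| 1 | 35% | 25% | 15% |
| 1.25 | 22% | 11% | 2% |

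For example, at k = 1.25 and r = 0.7: 1.5625 × 0.51 = 0.797, divided by 1 + 1.5625 - 1.75 = 0.8125, is 0.981, a saving of 2%.

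The difference between the two variances is (1 + k² - 2rk) - k²(1-r²) = (1 - rk)². It is never negative, so in large samples ANCOVA cannot do worse than the change score. The two tie only when rk = 1, that is, when the regression slope of follow-up on baseline is itself 1.

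**The case against.** The strongest reply is that nothing here is wrong. A t-test on change is unbiased in a randomised trial, this is an unpowered secondary outcome in a phase II study, and ANCOVA is an efficiency preference. That is right about validity, and it limits the point to precision. It does not remove the point, because the alternative uses the same data at almost no cost.

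The second reply is that the saving rests on quantities the documents do not give. That also stands. The 15% to 35% needs equal SDs as well as an assumed r; with k from 0.8 to 1.25 the range is about 2% to 50%. The figures describe the t-test only, and 16.46 also allows the Wilcoxon test.

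Three stronger readings are tempting, and the documents do not support them.

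- A reader might infer that excluding patients with missing data (16.8), with continuation past cycle 2 assumed to be 45% against 63% (16.3), biases the LASA comparison. Those rates count patients who start cycle 3, not forms returned. The C2D28 form is due before that and, by footnote 5 of 4.0, can be completed at home. Section 16.8 can naturally be read visit by visit. Bias is possible, but neither its presence nor its direction is established.
- A reader might infer that an unnamed visit inflates the false-positive rate. That requires someone to select the best of four visits, which the plan does not say will happen. It also requires a significance level for LASA, which the plan does not set: the one-sided 0.20 is stated for the primary endpoint only.
- A reader might infer that a repeated-measures model would cure missing-form problems. It assumes missing at random, so it does not remove bias if loss depends on unobserved current QOL. The case for changing the analysis is precision, not bias.

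**Conclusion.** The point holds as a nearly free improvement, not as an error. The planned LASA test is valid but uses the baseline score less efficiently than it could. Against the t-test on change, ANCOVA saves 35%, 25% or 15% of the variance at r = 0.3, 0.5 or 0.7 with equal SDs, and about 2% to 50% over the wider SD range. All of these rest on assumed r and SDs.

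That the saving is not negative in large samples is algebra and needs no assumption about r or k. Its size is uncertain until LASA data or an outside estimate of r and the SDs is available.

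The absence of a BFI analysis and of a named LASA visit is plain from the text, but these are missing details that the same edit fills. The primary endpoint and its sample size of 110 are unaffected.

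**What to change.** In 16.46, replace the unadjusted change-score test with ANCOVA of the post-baseline LASA score on baseline score, dosing strategy and PPES strategy, at one visit named in advance. C2D14 is a reasonable example: both arms are on drug then under the planned schedule, and it comes before C2D28. Alternatively, fit a repeated-measures model over C1D14, C2D1, C2D14 and C2D28 with the same baseline covariate and make the named visit the key contrast. Either version gives both comparisons in goal 2.24 from one model.

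Apply the same analysis to BFI. A BFI baseline is only inferred, because footnote 5 refers to appendices IV and V and the appendices are not in the text; if none is collected, fit the model without it.

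Report forms received against forms expected, by arm and visit. Booklet Compliance alone will not do this: 18.1 schedules it at evaluations during treatment, not at the end of treatment or in event monitoring. The off-treatment and death records are needed as well.

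The cost is SAP wording and modest programming, with no new data. The repeated-measures version carries two obligations: it assumes missing at random, and the SAP must say what it is meant to estimate for patients who stop treatment or die. ANCOVA at one visit is the simpler choice if the team prefers not to take these on, though it still uses only patients with a form at that visit.
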